6.5.1 Criteria for Early Withdrawal

Subjects may voluntarily withdraw from the study at any time. The PI may also discontinue a subject from the study at any time based on certain criteria. Reasons for PI-initiated discontinuation include:

- Pregnancy
- Inability to continue the exercise program

- Potential for harm to the participant

6.5.2 Follow-up Requirements for Early Discontinuation

There will be no follow-up once an individual completes or withdraws from the study. Data that was already collected from participants who discontinue will be used in analyses up to the point of discontinuation, and attempts will be made to collect data from participants at appropriate time points even after discontinuation of the exercise program.

6.5.3 Replacement of Early Withdrawal(s)

Subjects who prematurely withdraw will not be replaced unless withdrawal occurs prior to initiation of the exercise regimen.

7. STATISTICAL METHODS AND DATA ANALYSIS

7.1. Analysis of Safety

Safety will be continually assessed during each workout regimen by the exercise physiologist, and adjustments will be made to exercise performance during the workout to increase safety as per standard of care.

The AEs will be reviewed and assessed by the PI and reported per AHN IRB reporting requirements. Accidental disclosure of confidentiality is the only adverse event that would occur.

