3 PROTOCOL SYNOPSIS

3.1 Purpose:

This protocol seeks to analyze patient outcomes of the standard of care, monitored group exercise regimen of high-load resistance training and functional exercises with compound movements under close supervision on women who have been treated for breast cancer.

Primary Objective

- 1 Determine safety and feasibility measured by exercise compliance.

Exploratory Objectives

- 1 Determine changes in functional mobility testing changes at baseline, throughout, post-exercise assessment and 1 year after exercise assessment.
- 2 Determine quality of life at baseline, throughout, and post- exercise assessment
- 3 Determine changes in strength and load lifted at baseline, throughout, post-exercise assessment, and 1 year after exercise assessment.
- 4 Determine changes in resting metabolic rate at baseline, throughout, post- exercise assessment, and 1 year after exercise assessment.
- 5 Determine changes in body composition at baseline, throughout, post- exercise assessment and 1 year after exercise assessment, including body mass, fat mass, fat-free mass, % fat, and % fat-free mass.

Hypotheses

In this study, we hypothesize that an observed exercise regimen utilizing high-load resistance training initiated during or after cancer treatment is safe and feasible in women and may improve functional mobility, body composition, and resting metabolic rate.

3.2 Background and Significance:

Obesity is a risk factor for both breast cancer and disease recurrence after treatment.¹ Furthermore, weight gain during and after treatment for breast cancer is associated with a higher risk of recurrence, distant metastases, and death.² Yet, most women gain significant weight during and after breast cancer treatment, potentially compromising outcomes.

Contrary to these findings, activity levels have been repeatedly associated with a lower risk of breast cancer incidence, improved outcomes after breast cancer treatment, and improved breast cancer-specific and overall survival.³ The majority of breast cancer survivors do not meet adequate daily activity level recommendations, potentially compounding issues with weight gain during and after breast cancer treatment.⁴ As a result, attempts are underway to both quantify and increase activity levels during treatment and survivorship.⁵ Furthermore, and based on these findings, several areas of

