7.2 Analysis of Adherence

The primary feasibility endpoint will be session attendance and will be calculated as the proportion of participants completing at least 75% of the planned exercise sessions. Dropout rate, defined as individuals who quit the workout regimen altogether, is 20%. It is assumed that the rate of attendance will be similar in this pilot study. The 90% lower confidence bound (LCB) for the proportion of patients completing at least 75% of exercise sessions will be constructed. A 90% LCB $\geq .56$ will be considered a success (that is, the proportion of patients successfully completing the exercise regimen is at least 0.56 with 90% confidence). With 40 patients studied, a 90% LCB of 0.56 is associated with a completion rate of 0.7. Data from all participants will be analyzed for anthropometric, metabolic, fitness and QOL regardless of attendance level but a subgroup analysis will be performed using data from participants with $\geq 75\%$ attendance.

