8. SAFETY MONITORING AND REPORTING

8.1 Adverse Events and Serious Adverse Events:

Adverse events (AE) and serious adverse events (SAE) as a result of participating in the study are not expected because EXERT-BC is an observational study, including quality of life questionnaires.

From the time the subject signs the informed consent form through the exercise program completion visit, data will be collected for all AEs and SAEs recorded in the subject's medical record and adverse events case report form for summary reporting of the study's objective.

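### Safety is a primary objective, but its only named measure is exercise compliance, and section 7.1 says without qualification that a confidentiality breach is the only possible adverse event

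*Combined protocol and SAP*

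**What the plan says.** The primary objective in section 3.1 reads "Determine safety and feasibility measured by exercise compliance". The hypothesis in the same section is that "high-load resistance training initiated during or after cancer treatment is safe and feasible in women". Section 3.4 also calls the study a feasibility and safety registry.

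Section 7.2 assigns compliance to feasibility: "The primary feasibility endpoint will be session attendance". It supplies a definition (at least 75% of planned sessions), a 90% lower confidence bound and a success rule of 0.56.

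Section 7.1 covers safety analysis. It provides for observation during workouts, where "adjustments will be made to exercise performance during the workout to increase safety as per standard of care", and for review of AEs by the PI with reporting to the IRB. It then says "Accidental disclosure of confidentiality is the only adverse event that would occur". It names no AE summary.

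Section 8.1 has two paragraphs. The first says that AEs and SAEs resulting from study participation are not anticipated, because the study is observational. The second says "From the time the subject signs the informed consent form through the exercise program completion visit, data will be collected for all AEs and SAEs", taken from the medical record and the AE form, so that they can be summarised against the study's objective.

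**The concern.** The plan asks whether the regimen is safe and whether it is feasible, and it defines an answer only to the second question. If compliance is taken as the measure of safety, as 3.1 can be read, a good attendance figure would be reported as evidence that the exercise is safe. If the 7.1 sentence is taken at face value, exercise injury is ruled out before any data are seen, in the section meant to analyse it. Either route leads to a safety conclusion that cannot reflect injury from the exercise, although the AE data needed to answer the question are being collected.

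**Working it through.** **1. The plan's own precision figure.** The only one concerns feasibility: a completion rate of 0.70 in 40 patients, with a lower bound of 0.56 (section 7.2).
- Input: 0.70 × 40 = 28 completers.
- Exact (Clopper-Pearson) lower limit with 5% in the lower tail: the 0.05 quantile of Beta(28, 40 − 28 + 1) = Beta(28, 13), which is 0.5597. This rounds to 0.56, so the figure reproduces.
- No corresponding figure for safety exists to reproduce.

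**2. Can compliance stand in for safety?** Three classes a week for 12 weeks (section 5.3) give 3 × 12 = 36 sessions, so the 75% threshold is 0.75 × 36 = 27. A participant who is injured but attends 27 sessions counts as a success. A participant who stops uninjured after a few weeks counts as a failure. The endpoint can therefore take any value whatever the number of injuries. It is a sound feasibility measure, but it carries no direct information on harm.

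**3. The 7.1 sentence beside the other text.**
- Section 8.1, second paragraph: all AEs and SAEs are collected, with no restriction to data handling. This is the direct conflict.
- Section 3.2: earlier exercise studies reported self-limiting musculoskeletal problems such as strains and tendinitis. The section adds that AEs are minimal overall. Minimal is not the same as none.
- Section 6.5.1: possible harm to the participant is a reason for the PI to withdraw someone.
- Section 7.1 itself: exercise is adjusted during the workout for safety, which presupposes that exercise can cause harm.
- Section 8.1, first paragraph: this partly agrees with 7.1, but it is restricted to events caused by taking part in the study. The 7.1 sentence has no such restriction.

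**4. What a safety estimate of this size could show.** The documents give no safety event rate or confidence level. I assume a proportion of participants with at least one event and an exact two-sided 95% interval. I take the number of starters as 40 to 43, because section 3.5 accrues 43 to obtain 40 and section 6.5.3 allows replacement only before the regimen begins.
- With 0 events, upper limit = 1 − 0.025^(1/n).
- n = 40: 1 − 0.025^(1/40) = 0.0881, or 8.8%.
- n = 43: 1 − 0.025^(1/43) = 0.0822, or 8.2%.
- Hypothetical count of 4 participants with an event: 4/40 = 10.0% (2.8% to 23.7%), or 4/43 = 9.3% (2.6% to 22.1%).
- Chance of seeing at least one event among 40 = 1 − (1 − p)^40: 33% if the true proportion is 1%, 55% if 2%, and 87% if 5%.

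An event-free study would thus be compatible with a true proportion of up to about 8 to 9%. The choice between 40 and 43 changes this very little.

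**The case against.** The strongest defence is that the exercise is standard of care and the study is a registry, so the 7.1 sentence was meant to cover only risk added by the research. Sections 3.4, 5.2, 5.3 and 6.2 describe the study this way, and the first paragraph of 8.1 points in the same direction. This is plausible and probably what was intended. It does not remove the point. The qualifier is absent from 7.1, and if it were there, 7.1 would address data handling while the objective and hypothesis concern the safety of high-load training.

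A second defence is that 8.1 already fixes which events are collected, from which sources and over what period. That stands, and a reader who infers that the plan has no safety data is mistaken. What is missing is the link from those data to the objective.

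A reader might also infer that the safety proportion could be calculated only in those who remain, or only in those with at least 75% attendance, so that injuries among early stoppers disappear. The documents do not support this. Sections 6.5 and 6.5.2 keep and use data from people who discontinue, and 6.5.2 adds that collection will be attempted at the planned times after someone stops the programme. Section 8.1 counts events from consent. The attendance subgroup in 7.2 is additional to "Data from all participants will be analyzed for anthropometric, metabolic, fitness and QOL regardless of attendance level", and that sentence does not concern AEs. Nor does any section say that injured participants are more likely to stop: 3.2 calls the known events self-limiting, and 7.1 adjusts exercise so that people can continue.

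The missing denominator and interval would, taken alone, be a matter of detail. They belong here because the safety measure has to be named anyway.

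**Conclusion.** The point holds and should be fixed. Two pieces of text are wrong as written: 3.1 names compliance as the only measure for an objective that includes safety, and 7.1 rules out every adverse event except a confidentiality breach. The second conflicts directly with the collection of all AEs and SAEs in 8.1 and does not fit 3.2 or 6.5.1. It does not conflict with the whole protocol, since the first paragraph of 8.1 partly agrees with it.

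This conclusion rests on the text and needs no calculation. The figures only show how much a safety result could say: with no events, an upper limit of 8.8% (40 starters) or 8.2% (43 starters), assuming an exact two-sided 95% interval. The documents do not show that early stoppers would be left out of the safety count, and the conclusion does not rely on that.

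**What to change.** - **Section 3.1:** state that feasibility is measured by attendance, and safety by the AEs and SAEs collected under 8.1.
- **Section 7.1, the disputed sentence:** delete it, or limit it to risk added by research data handling.
- **Section 8.1, first paragraph:** make the same limit explicit, so that it is not read as covering the exercise.
- **Section 7.1, reporting:** among all participants who start the programme, including those who stop early, give the number and proportion with at least one AE, at least one exercise-related AE and at least one SAE. Use the existing 8.1 window. Show events before the first session, including any during baseline testing, as a separate row. Give an exact two-sided 95% interval for each proportion, and list events by type and by whether they led to stopping.
- **Section 7.1, interpretation:** describe the safety result as descriptive, and state that zero events would leave an upper limit of 8.8% with 40 starters or 8.2% with 43.

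Cost: wording in three sections, one extra table with a listing, and possibly one attribution field on the AE form. AEs are already collected and reviewed by the PI, and reasons for discontinuation are already recorded, so no visit or procedure is added. The safety statement becomes more modest. AE data on early stoppers may be incomplete, and the report should say so.

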7.2 Analysis of Adherence

The primary feasibility endpoint will be session attendance and will be calculated as the proportion of participants completing at least 75% of the planned exercise sessions. Dropout rate, defined as individuals who quit the workout regimen altogether, is 20%. It is assumed that the rate of attendance will be similar in this pilot study. The 90% lower confidence bound (LCB) for the proportion of patients completing at least 75% of exercise sessions will be constructed. A 90% LCB $\geq .56$ will be considered a success (that is, the proportion of patients successfully completing the exercise regimen is at least 0.56 with 90% confidence). With 40 patients studied, a 90% LCB of 0.56 is associated with a completion rate of 0.7. Data from all participants will be analyzed for anthropometric, metabolic, fitness and QOL regardless of attendance level but a subgroup analysis will be performed using data from participants with $\geq 75\%$ attendance.

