Exercise class attendance will be recorded. Workout regimens, including exercise type, sets, and repetitions will be recorded to aid in workout consistency and progression and to calculate load lifted. Initial strength assessment will occur during the initial two weeks of the workout regimen to help ascertain proper weight usage. Repetition schemes to mimic basic exercise principles for hypertrophy, strength, and power based on 1-repetition maximum (1RM) extrapolation and repetition range charts after assessing each exercise performed to near repetition fatigue/voluntary failure (i.e. when a repetition or safe lifting form can no longer be maintained while monitored by exercise physiologist).

Weight lifted, repetitions, sets, and notes will be recorded and utilized to estimate intensity via volume load calculations (volume load = weight lifted \times repetitions \times sets). An example of a workout is listed below.

Day One (anterior muscle closed-chain compound exercise focus):

A1: Split Squat 4X6 week 1-4, 4X4 weeks 5-8, 4X2 week 9-12

A2: Side plank 3X20 seconds each side week 1-6, 3X30 seconds each side week 7-12

B1: Bird dog row 3X10 week 1-6, 3x12 week 7-12

B2: Feet elevated glute bridge 3X10 week 1-6, 3x12 week 7-12

B3: Half Kneeling 1 arm overhead press 3X10 week 1-6, 3x12 week 7-12

Day Two (posterior muscle closed-chain compound exercise focus):

A1: Trap bar (or straight bar) Deadlift 4X6 week 1-4, 4X4 weeks 5-8, 4X2 week 9-12

A2: Band pull-aparts 3X10 week 1-6, 3x12 week 7-12

B1: Goblet squat 3X10 week 1-6, 3x12 week 7-12

B2: Incline bench press 3X10 week 1-6, 3x12 week 7-12

B3: Tall kneeling front raise 3X10 week 1-6, 3x12 week 7-12

Day Three (strength/hypertrophy focus):

A1: Bent over row 4X6 week 1-4, 4X4 weeks 5-8, 4X2 week 9-12

A2: Pushups (use bar to raise up height if needed) 3X10 week 1-6, 3x12 week 7-12

B1: Weighted hip bridge 3X10 week 1-6, 3x12 week 7-12

B2: Step ups 3X10 week 1-6, 3x12 week 7-12

B3: Farmers carries 3X10 steps each leg week 1-6, 3X12 steps each leg week 7-12

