6. PATIENT ASSESSMENTS

Table 1: Participant Assessments

Assessment	Screening	Baseline Assessments (Prior to Program)	During Exercise Program	At Exercise Program Completion	1 Year After Exercise Program Completion
Consent	X				X ^f
History/Physical	X				
Weight, height, and BMI	X			X	X
Body Composition Assessment ^a		X		X	X
Resting Metabolic Rate Assessment		X		X	X

QOL and Exercise Forms ^b		X		X	X
Strength Assessment ^{c,d}		X	X	X	X
Mobility Assessment ^c		X		X	X
Compliance ^e			X		

- a To calculate lean and fat mass and percentages, and total energy expenditure (kcal/day) SOC
- b EQ-5D-5L, and Leisure-Time Exercise Questionnaire SOC
- c Functional Mobility Survey and Y-balance test, includes grip strength SOC
- d Will also occur periodically throughout program to adjust exercise regimen SOC
- e Attendance collected at each workout
- f Verbally reconsent to use SOC data for research purposes

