Subject names or identifiers will not be used in reports, presentations at scientific meetings, or publications in scientific journals.

Data Collection:

The following data will be stored in the secure database:

- Age
- Diagnosis
- Weight, height, and BMI
- Comorbid medical conditions
- Surgical procedure for breast cancer or orthopedic procedures
- Type of hormonal therapy
- Body composition at start/completion (body fat percentage, % fat-free mass, fat mass, fat-free mass, body mass)
- Resting metabolic rate at start/completion
- Exercise details (specific exercise, repetitions, weight, load lifted)
- FMS and Y-balance test
- Grip strength at start/completion
- QOL forms (EQ-5D-5L)
- Godin Leisure-Time Exercise Questionnaire
- Adherence rates (percentage classes)
- Assessments that are SOC

10.5 Protocol Amendments:

All protocol amendments must be initiated by the Principal Investigator and approved by the IRB prior to implementation. IRB approval is not required for protocol changes that occur to protect the safety of a subject from an immediate hazard. However, the Principal Investigator must inform the IRB and all other applicable regulatory agencies of such action immediately.

10.6 Records Retention:

The Principal Investigator will maintain study-related records for the longer of a period of at least six years after study completion, or per AHN policy, whichever is more strict.

APPENDICES

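### The feasibility success rule counts class attendance only, so it cannot by itself support a conclusion that high-load training is feasible

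*Combined protocol and SAP*

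**What the plan says.** The primary objective in 3.1 is "Determine safety and feasibility measured by exercise compliance", and the hypothesis is that "an observed exercise regimen utilizing high-load resistance training initiated during or after cancer treatment is safe and feasible in women".

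Compliance is class attendance wherever it is made operational:
- Section 7.2: "The primary feasibility endpoint will be session attendance and will be calculated as the proportion of participants completing at least 75% of the planned exercise" classes.
- Table 1, footnote e to the compliance row: "Attendance collected at each workout".
- Section 10.4: adherence is stored as a percentage of classes.

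Section 7.2 declares success if the 90% lower confidence bound for this proportion is at least 0.56. In parentheses it explains this as the proportion of patients who have successfully completed the regimen.

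Sections 5.2 and 5.3 say workouts are continually adjusted, for progression as well as for safety. Section 7.1 adds that "adjustments will be made to exercise performance during the workout to increase safety as per standard of care".

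Load is not ignored. Section 5.3 says "Weight lifted, repetitions, sets, and notes will be recorded" and used for volume load. Appendix III recalculates loads every four weeks after week 3, and exploratory objective 3 is change in strength and load lifted. The data list in 10.4 includes "Exercise details (specific exercise, repetitions, weight, load lifted").

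**The concern.** The rationale in 3.3 is that earlier programmes often relied on light weights and many repetitions, and that heavier compound training is little tested in these women. Load is what sets this regimen apart, and the success rule does not see it. A woman whose weights are lowered, or whose exercises are swapped, at every visit contributes exactly as much to success as one who completes everything planned. The documents do not say that a modified session counts differently. They give no numerical meaning for high-load and plan no comparison of planned with delivered work.

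Two conclusions are at stake. A pass shows that women came to supervised classes, which a lighter programme might also achieve. And if reductions made for tolerability are not summarised, a statement that the regimen was safe may describe a modified regimen without saying so. With a single arm, no comparison group helps to separate these readings.

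**Working it through.** **Inputs.** From 7.2: n = 40, success if the 90% lower bound is at least 0.56, and a bound of 0.56 said to go with an observed rate of 0.7. From 5.3: three classes a week. From 3.6: 12 weeks. From Appendix III: a two-week run-in.

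**Sessions.** 3 × 12 = 36 planned; 75% of 36 = 27. The run-in covers 3 × 2 = 6, leaving 30.

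**The plan's own figure.** The exact (Clopper-Pearson) lower limit for x of n is the α quantile of a Beta(x, n − x + 1) distribution. For 28/40 = 0.70:
- α = 0.05 (lower end of a two-sided 90% interval): 0.5597, which rounds to the stated 0.56.
- α = 0.10 (one-sided 90% bound): 0.588.

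The stated figure is therefore reproduced by the two-sided 90% limit. Section 7.2 does not say which bound is meant, so both are shown below.

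**Dependence on delivered work.** Take the rule as at least 28 of 40. With true attendance probability p, the chance of success is P(X ≥ 28), X ~ Binomial(40, p). At p = 0.80 this is 0.957. No load term enters, so it is 0.957 whether all attenders train at the planned load or none do.

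For contrast only, suppose a woman counted only if she also received the planned work, and a share q of attenders did. The probability per woman is then 0.80 × q:

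| q (assumed) | 0.80 × q | Chance of at least 28/40 | Attendance rule |
|---|---|---|---|
| 1.0 | 0.80 | 0.957 | 0.957 |
| 0.9 | 0.72 | 0.684 | 0.957 |
| 0.8 | 0.64 | 0.269 | 0.957 |
| 0.7 | 0.56 | 0.050 | 0.957 |

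**One observed result.** Assume 30 of 40 women reach 75% attendance:

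| Share of the 30 receiving planned work (assumed) | Count | One-sided 90% bound | Two-sided 90% lower limit |
|---|---|---|---|
| 100% (the same as attendance alone) | 30/40 | 0.641 | 0.613 |
| 90% | 27/40 | 0.5625 | 0.534 |
| 80% | 24/40 | 0.486 | 0.458 |

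Measured against 0.56, attendance passes on either bound. At 90% delivery the answer depends on the bound: 0.5625 is above and 0.534 below. At 80% both are below. The gap between attending and receiving the work can matter, but its size here is unknown.

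**The case against.** The strongest reply is that attendance is a reasonable primary feasibility endpoint for a single-arm registry of a supervised standard-of-care programme in which individual adjustment is intended, upward as well as downward. That stands, and it is why attendance should remain the success rule. Making delivered work a second hurdle would also change the trial's chance of success sharply (0.957 to 0.684 or 0.269 in the first table), on a threshold the documents do not supply.

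A second reply is that load is already a study outcome. It is, under exploratory objective 3. But that objective concerns change over time, with no target. Section 7.3 does not name load and tests change from baseline. Average load can rise while many women do not complete what was planned for them.

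A reader might infer more than the documents support:
- *That load data are not collected.* They are (5.3, Appendix III, 10.4). Sets are not named in 10.4, but load lifted is weight × repetitions × sets, so they can largely be recovered for weighted exercises.
- *That the load will not be delivered.* No delivery rate is given; the 90% and 80% above are assumptions.
- *That the schedule is mostly not heavy lifting.* In 5.3 only the three A1 lifts use six or fewer repetitions: 3 × 4 = 12 of 48 weekly sets. But that schedule is labelled an example, and it applies equally to a woman who does all of it. It says nothing about attendance versus delivery.

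**Conclusion.** The point holds as a mismatch between the success rule and the conclusion drawn from it. The rule is a function of attendance only. It can support a statement about attending at least 75% of planned classes, but not, alone, that "high-load resistance training initiated during or after cancer treatment is safe and feasible in women". What is missing is a pre-specified comparison of planned with delivered work and a link from it to the conclusion. The basic load data are kept.

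No stated figure is wrong on this account. The illustration rests on assumed attendance and delivery shares, on n = 40, and, at 90% delivery, on which bound 7.2 intends. This is a worthwhile, inexpensive improvement; it does not invalidate the primary endpoint.

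**What to change.** Keep attendance, with the 90% lower bound of at least 0.56, as the primary endpoint and success rule. Then:

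1. **Add to 7.2 a secondary, descriptive delivered-dose measure.** For each woman, among sessions attended after the two-week run-in, take the share of planned sets × repetitions completed at or above the weight planned for her under the progression rule, before any safety adjustment. Using the weight set after an adjustment would hide the reductions of interest. Score unweighted and timed exercises on sets and repetitions or time only. Report the distribution, with no pass mark.
2. **Do not count missed sessions again.** A woman attending all 6 run-in sessions and 21 of the other 30 meets 27/36 = 75%. If missed sessions scored zero, her dose could not exceed 21/30 = 70% even with every attended session completed in full.
3. **Report modifications.** Give the share of women and of sessions with a load reduction or substitution for symptoms or safety, using the recorded notes. Add planned weight and reason for modification to the 10.4 list.
4. **Align the wording.** In 7.2, describe the success criterion as attending at least 75% of planned sessions, in place of the parenthetical reference to completing the regimen. State that any conclusion about high-load training must be read with the delivered-dose result, using a meaning of high-load that the sponsor fixes before analysis.

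The cost is some transcription from the logs, two data fields not now listed in 10.4, and a compliance picture that may look less favourable than attendance alone. The primary decision and its power are unchanged.

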3.5 Selection of Subjects and Sample Size:

Women ages 20-89 treated for ductal carcinoma in situ or invasive carcinoma will be considered for this trial.

The accrual goal is 43 subjects to achieve a sample size of 40 subjects, allowing for enrolled subjects who are unable to be complete the exercise program. Estimated accrual and completion time is approximately 2 years.

3.6 Duration of Study:

Subjects will be on study for an approximate 15 months, with the exercise program encompassing 12 weeks and an assessment following 1 year after the exercise program. Thereafter subjects will continue to be followed by the treating medical oncologist and/or radiation oncologist per standard of care (SOC) for follow up care but utilizing the data for research purposes.

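### The completion rate of 0.7 given for a 90% lower bound of 0.56 does not fit the success rule as worded, which 27 of 40 (0.675) already meets

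*Combined protocol and SAP*

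**What the plan says.** Section 7.2 (Analysis of Adherence) makes session attendance the primary feasibility endpoint, "calculated as the proportion of participants completing at least 75% of the planned exercise sessions". On the analysis it says: "The 90% lower confidence bound (LCB) for the proportion of patients completing at least 75% of exercise sessions will be constructed". The decision rule is "A 90% LCB $\geq .56$ will be considered a success", and a parenthesis gives its meaning: "the proportion of patients successfully completing the exercise regimen is at least 0.56 with 90% confidence".

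One worked value follows: "With 40 patients studied, a 90% LCB of 0.56 is associated with a completion rate of 0.7". Section 3.5 is the source of the 40: "The accrual goal is 43 subjects to achieve a sample size of 40 subjects".

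Section 7.2 names no interval method, does not say whether the bound is one-sided or two-sided, gives no rounding rule and states no minimum number of completers. No other section supplies these.

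**The concern.** A lower bound that the true proportion exceeds with 90% confidence is a one-sided 90% bound, with 10% in the lower tail. The worked value should then be the completion rate at which that bound reaches 0.56 with 40 patients. A rate of 0.7 is 28 of 40, and the one-sided 90% bound there is clearly above 0.56.

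The 0.7 is an illustration, not a second criterion. It is, however, the only number that shows a reader how the rule works in patients. Someone who takes it as the pass mark applies a stricter rule than the one worded. Because method and sidedness are open, the cut-off could be read as 27, 28 or 29 completers, and the choice could be made after the attendance data are known.

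**Working it through.** **Inputs** (section 7.2): n = 40; threshold 0.56; confidence 90%; stated completion rate 0.7, so x = 0.7 × 40 = 28.

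**Formulas.** With a the lower-tail probability, z the standard normal quantile at 1 − a, and p = x/n:

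- Clopper-Pearson (exact): L solves P(X ≥ x | n, L) = a, so L is the a-quantile of Beta(x, n − x + 1).
- Wald: L = p − z·√(p(1 − p)/n).
- Wilson: L = [p + z²/(2n) − z·√(p(1 − p)/n + z²/(4n²))] / (1 + z²/n).

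**Step 1. The plan's own pair, 28/40 and 0.56.** For a one-sided 90% bound, a = 0.10 and z = 1.2816. Wald gives 0.70 − 1.2816 × √(0.70 × 0.30/40) = 0.70 − 1.2816 × 0.07246 = 0.607. The lower bounds at 28/40 are:

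| Method | a = 10% (one-sided 90%) | a = 5% (lower limit of two-sided 90%) | a = 2.5% (lower limit of two-sided 95%) |
|---|---|---|---|
| Clopper-Pearson | 0.5884 | 0.5597 | 0.5347 |
| Wilson | 0.6008 | 0.5713 | 0.5457 |
| Wilson, continuity-corrected | 0.5878 | 0.5584 | 0.5329 |
| Wald | 0.6071 | 0.5808 | 0.5580 |
| Wald, continuity-corrected | 0.5946 | 0.5683 | 0.5455 |
| Jeffreys | 0.6015 | 0.5729 | 0.5478 |
| Agresti-Coull | 0.6004 | 0.5706 | 0.5447 |

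No entry in the 10% column is 0.56. Three of the 21 entries round to 0.56: 0.5597, 0.5584 and 0.5580. All three have less than 10% in the lower tail and all are below 0.56, so under each of them the rule applied unrounded needs 29/40 (for Clopper-Pearson at 5%, 29/40 gives 0.5861).

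**Step 2. Where the rule as worded is first met** (one-sided 90%):

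| Completers | Rate | Clopper-Pearson | Range over the seven methods | Bound ≥ 0.56? |
|---|---|---|---|---|
| 26 | 0.650 | 0.5368 | 0.5365 to 0.5534 | No, all methods |
| 27 | 0.675 | 0.5625 | 0.5620 to 0.5801 | Yes, all methods |
| 28 | 0.700 | 0.5884 | 0.5878 to 0.6071 | Yes, all methods |

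Mid-P and logit bounds agree (27/40: 0.5741 and 0.5740; 26/40: 0.5483 and 0.5484). If the count is treated as continuous, the rate at which the one-sided 90% bound equals exactly 0.56 is 0.656 to 0.673, depending on the method.

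**Step 3. What the choice of cut-off changes** (exact binomial, n = 40). The rate 0.80 is an assumption, 1 minus the 20% dropout in section 7.2. The true completion rate could be lower, since a participant can stay in the programme and attend fewer than 75% of sessions.

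| Minimum completers | False success at 0.56 | Exact confidence for 0.56 | Success at 0.70 | Success at 0.80 |
|---|---|---|---|---|
| 27 | 0.0947 | 1 − 0.0947 = 0.9053 | 0.7032 | 0.9806 |
| 28 | 0.0504 | 1 − 0.0504 = 0.9496 | 0.5772 | 0.9568 |
| 29 | 0.0242 | 1 − 0.0242 = 0.9758 | 0.4406 | 0.9125 |

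The 27 and 28 readings disagree only if X = 27. The probability is 0.7032 − 0.5772 = 0.126 at a true rate of 0.70, and 0.9806 − 0.9568 = 0.024 at 0.80.

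**Step 4. If all 43 accrued are analysed.** The one-sided 90% exact bound is 0.5425 at 28/43 and 0.5664 at 29/43, so the worded rule would need 29. A bare count of 27 or 28 does not carry over to another denominator.

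**The case against.** The strongest reply is that section 7.2 never says one-sided. A 90% lower bound can be read as the lower limit of an ordinary two-sided 90% interval. With the exact method that limit at 28/40 is 0.5597, which is 0.56 at the plan's two-decimal precision. This is probably where the 0.7 came from, so it need not be a slip in arithmetic. But that limit leaves 5% in the lower tail and is a 95% lower bound, which does not match the plan's own explanation in terms of 90% confidence. It also reaches 0.56 only by a rounding that the plan does not mention.

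A second reply is that 0.7 has one decimal, and 0.675 rounds to 0.7. The author might have meant 27/40 with its exact bound of 0.5625. The text does not exclude this. But at one decimal 0.7 covers 27/40 (0.675), 28/40 (0.700) and 29/40 (0.725) alike, so on this reading the worked value fails to identify the pass mark.

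It can also be said that the effect is small, that a reader who uses 28 errs on the cautious side, and that moving the mark to 27 raises the false-success probability at 0.56 from 5.0% to 9.5%. All of that stands. A success at 28/40 still holds at 90% confidence, and the documents do not show whether the sponsor planned around 0.7 or around a 10% error. This limits the severity and is why the fix includes a route that keeps 28. It does not make 0.7 and the worded rule agree.

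**Conclusion.** The concern holds. Under the rule as the plan explains it, 27 of 40 is enough, and the stated 0.7, taken as 28/40, has a one-sided 90% bound of 0.588 to 0.607 rather than 0.56. This does not depend on the interval method. It rests on reading the parenthesis as a one-sided 90% statement, which is its natural meaning, and on a denominator of exactly 40.

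The size is modest: one patient between the worded rule and the worked value, or two if a two-sided 90% exact limit is applied unrounded. It should still be corrected, because the pass mark of the primary feasibility endpoint ought to be fixed before the attendance counts are known.

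**What to change.** In section 7.2, name the bound, say that it is applied unrounded, and give the minimum count. There are two ways to do this:

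1. **Preferred, because it keeps the rule and its explanation.** Replace the sentence containing 0.7 with: *Success requires a one-sided 90% Clopper-Pearson lower bound of at least 0.56, applied without rounding; with 40 patients this means at least 27 completers (0.675, bound 0.5625).*
2. **If the sponsor wants 28/40.** State the minimum of 28 completers directly as the rule and report its one-sided 90% exact bound as 0.588. Do not claim 95% confidence for 0.56, because the probability of 28 or more at a true rate of 0.56 is 0.0504, just above 5%.

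In either case, add what happens if the number analysed is not 40. Under option 1 the same unrounded bound is applied to the actual number (29 of 43, for example). Under option 2 the sponsor needs to say how the count is to be adapted.

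The cost is one sentence in section 7.2, with no extra patients or data. The choice should be made before the attendance results are known.
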